8.2 Blinding

This is an open label trial with no blinding.

8.3 Formulation of Test and Control Products

8.3.1 Mucolox™

Description

Mucolox™ (PCCA, Houston, TX 77099) is a mucoadhesive polymer designed to improve mucoadhesion and prolong retention of medications at application sites within the oral mucosa. The composition of Mucolox™ is outlined in the table below.

Ingredient Name	INCI Name/Technical Name	Classification	FDA Reference
Potassium Sorbate NF	Potassium Sorbate	Subpart D – Chemical Preservatives	21 CFR 582.3640
Sodium Benzoate NF	Sodium Benzoate	Subpart D – Chemical Preservatives	21 CFR 582.3733
Glycerin USP (Natural)	Glycerin	Subpart B – General Purpose Food Additive	21 CFR 582.1320
Edetate Disodium USP Dihydrate	Disodium EDTA	FDA has no questions regarding intended use.	GRN000363
Pullulan	Pullulan	FDA has no questions regarding intended use in certain foods.	GRN000099
Tamarindus Indica Seed Polysaccharide	Tamarindus Indica Seed Polysaccharide	FDA has no questions regarding intended use.	GRN000503
Isomalt	Isomalt	Self-Determined GRAS (1996)	GRN6G0321
Simethicone USP	Simethicone	Used in Various Routes, Dosage Forms and Maximum Potencies	UNII: Multiple (Mixture)
Sodium Hyaluronate	Sodium Hyaluronate	Used in Various Routes, Dosage Forms and Maximum Potencies	UNII: YSE9PPT4TH
Poloxamer 407	Poloxamer 407	Used in Various Routes, Dosage Forms and Maximum Potencies	UNII: TUF2IVW3M2
Zea Mays (Corn) Starch	Zea Mays (Corn) Starch	Used in Various Routes, Dosage Forms and Maximum Potencies	UNII: O8232NY3SJ
Carbomer	Carbomer	Used in Various Routes, Dosage Forms and Maximum Potencies (Type: Proprietary)	UNII: Type Proprietary
Water	Water	N/A	UNII: 059QF0K00R

Compatibility

N/A

Handling

There are no special handling requirements.

Availability

Compounded dexamethasone solution in Mucolox™ will be dosed at a concentration of 0.5 mg/5mL and dispensed through the UCSF Investigational Drugs Services Pharmacy. The prescription for the patients in ARM B (dexamethasone) will also be dispensed through the UCSF Investigational Drugs Services Pharmacy.

Preparation

Study subjects will be given a kit with the following, including detailed written instructions (see Appendix 1):

ARM A

- A four week supply of compounded dexamethasone solution in Mucolox™ will be dispensed, with extra for error and spillage, which will be rounded to 480 mL bottle at a concentration of 0.5 mg/5mL.
- Small dosing cups

Administration

Subjects will be instructed to rinse with 5 ml of compounded dexamethasone solution in Mucolox™ (0.5 mg/5ml; ARM A) for 5 minutes. After 5 minutes, subjects will be instructed to expectorate and to not eat or drink for 15 minutes after. The rinses will be completed three times per day, equally spaced during awake hours. If a study rinse is missed, subjects will be asked to attempt to make up for the missed rinse later the same day, to maintain four rinses per day. If necessary, for example, two consecutive 5-minute rinses can be completed at night before bed. This does not pose any known safety risk.

Ordering

Study rinses will be ordered through the UCSF Investigational Drugs Services Pharmacy.

Availability

Dexamethasone 0.5mg/5mL solution in Mucolox will be compounded and dispensed through the UCSF Investigational Drugs Services Pharmacy.

Destruction and Return

[figure not shown]
Patients should not continue to use any unused study supply once they have completed the study. It should be returned to the investigator and will be sent to pharmacy for destruction.

8.4 Dexamethasone solution

Description

Dexamethasone (NDC 00054-3177-63; Roxane Laboratories, Columbus, OH 43216-6532) is a synthetic adrenocortical steroid commercially available as a 0.5mg/5mL solution. It is stable in air and practically insoluble in water.

- The molecular weight is 392.47.
- The molecular formula is $C_{22}H_{29}FO_5$
- The structural formula is:

Each 5 mL of oral solution contains 0.5 mg of dexamethasone and citric acid, disodium edetate, flavoring, glycerin, methylparaben, propylene glycol, propylparaben, sorbitol and water.

Storage and Stability

Dexamethasone solution is stable at room temperature for 30 days after opening per package insert.

Compatibility

N/A

Handling

There are no special handling requirements.

Availability

Dexamethasone 0.5mg/5mL solution will be dispensed through the UCSF Investigational Drugs Services Pharmacy.

Preparation

Study subjects will be given a kit with the following, including detailed written instructions (see Appendix 1):

ARM B

- A four-week supply of dexamethasone solution will be dispensed, with extra for error and spillage, which will be rounded to 480 mL bottle at a concentration of 0.5 mg/5mL.
- Small dosing cups

Administration

Subjects will be instructed to rinse with 5 ml of the prescribed dexamethasone 0.5mg/5ml solution (ARM B) for 5 minutes. After 5 minutes, subjects will be instructed to expectorate and to not eat or drink for 15 minutes after. The rinses will be completed three times per day, equally spaced during awake hours. If a study rinse is missed, subjects will be asked to attempt to make up for the missed rinse later the same day, to maintain four rinses per day. If necessary, for example, two consecutive 5 minute rinses can be completed at night before bed. This does not pose any known safety risk.

Ordering

Dexamethasone solution will be ordered through the UCSF Investigational Drugs Services Pharmacy.

Destruction and Return

Patients should not continue to use any unused study supply once they have completed the study. It should be returned to the investigator for destruction.

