PRIMARY OBJECTIVE	The primary objective of this study is to determine the clinical efficacy and tolerability of compound dexamethasone at 0.5 mg/5 mL in Mucolox™ for the treatment of Oral Inflammatory Ulcerative Diseases as measured by a reduction in oral symptoms between patients treated with compounded dexamethasone 0.5mg/5ml solution in Mucolox™ (group A) and patients treated with topical commercial dexamethasone 0.5mg/5ml solution only (group B).
SECONDARY OBJECTIVES	The secondary objectives are: 
 • To determine the clinical improvement in clinician-reported outcome measures achieved by treatment with topical compounded dexamethasone at 0.5 mg/5 mL in Mucolox™ compared to commercial dexamethasone 0.5mg/5ml solution alone. • To assess the tolerability of Oral Inflammatory Ulcerative Diseases as measured with the 14-item Oral Health Impact Profile (OHIP-14).
NUMBER OF SUBJECTS	30
SUBJECT SELECTION	Inclusion Criteria:

CRITERIA
	
Age 18 years and older.
 
Patients with symptomatic biopsy proven Oral Inflammatory Ulcerative Diseases (worst VAS sensitivity score ≥ 7 over the last week).
 
Ability to understand and the willingness to sign a written informed consent document.
 
Exclusion Criteria: Patients already on topical or systemic steroids.
 
Inability to comply with study instructions.
 
Uncontrolled intercurrent illness or psychiatric illness/social situations that would limit compliance with study requirements.
 
VAS sensitivity score < 7.
 
Pregnant women. A urine pregnancy test will be performed for women of child bearing potential.
 
Allergy to fluconazole
 
Patients on medications that have a strong interaction with fluconazole
 
Patients with advanced liver disease

TEST PRODUCT, DOSE, AND ROUTE OF ADMINISTRATION
	
Dexamethasone 0.5 mg/5mL in Mucolox compounded oral solution swish and spit TID for 4 weeks

CONTROL PRODUCT, DOSE AND ROUTE OF ADMINISTRATION
	
Dexamethasone 0.5 mg/5mL (NDC 00054-3177-63; Roxane Laboratories, Columbus, OH 43216-6532) oral solution swish and spit TID for 4 weeks

DURATION OF SUBJECT PARTICIPATION AND DURATION OF STUDY
	
Subjects will be on study for up to 28 days
 
Screening: day 0
 
Treatment: 28 days
 
Follow-up: Day 28 \pm 5 days
 
The total duration of the study is expected to be 4 weeks.

CONCOMITANT MEDICATIONS	Allowed: all Prohibited: none

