2.1 Risk / Benefit Assessment

2.1.1 Drug side effects and toxicities

Potential side effects with dexamethasone 0.5mg/5mL solution used as an oral topical rinse include an increased risk of developing oropharyngeal candidiasis and systemic absorption. All patients will be prescribed antifungal prophylaxis while on study with fluconazole 200 mg once a week. All participants will be informed that they may withdraw from the study at any time. As a topically applied agent, dexamethasone therapy can be discontinued at any time without any complications. Any noted clinical response will be expected to be reversed in such situations.

Prolonged application of potent topical corticosteroids (e.g., > 50 g of clobetasol propionate or > 500 g of hydrocortisone per week) may lead to short-term hypothalamic-pituitary-adrenal axis alteration. In our study, in case of any systemic absorption, the maximum dose would be 10.5 mg/week (5 mL x 0.1 mg/mL = 0.5 mg/rinse, 3 times/day = 1.5 mg, 7 days/week = 10.5 g). We do not expect there to be significant systemic absorption, and therefore do not expect systemic side

effects of dexamethasone solution when used as a swish and spit. Mucolox™ is a vehicle for drug delivery used in compounding medications with ingredients expected to be harmless. No major side effects from dexamethasone 0.5mg/5mL solution and dexamethasone 0.5mg/5mL solution in Mucolox™ use were reported in our first preliminary study³¹.

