9.3 Study Agents Administration

The Investigator or co-investigators will prescribe the study drug in the clinic and instruct the patient on study drug use. Both dexamethasone compounded 0.5mg/5ml solution in Mucolox™ and commercial dexamethasone solution will be dosed topically at a concentration of 0.5 mg/5mL.

A four week supply will be dispensed. The treatment instructions will be to rinse and spit (NOT swallow) with one teaspoon (5 mL) of the solution, three times a day for 5 minutes at a time, and not to eat or drink for 15 minutes afterwards. Subjects will maintain a diary (Appendix 2) and record each dose, the length of time rinsing, and any adverse effects.

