Appendix 1**INSTRUCTIONS FOR PREPARING & USING YOUR
TOPICAL SOLUTION****WHAT YOU WILL RECEIVE**

- One 480 mL bottle of concentrated solution (5 mg/5 mL)
- 4 tablets of fluconazole 200 mg

USING YOUR SOLUTION

You will be rinsing with your solution **3 times per day**.

1. Gently shake the bottle of solution.
2. Pour 5 mL of solution into the dosing cups provided.
3. Swish the solution in your mouth for 5 minutes, then spit – DO NOT SWALLOW!
4. Do not eat or drink for 15 minutes after rinsing.

Please take one table of fluconazole once a week

CONFIDENTIAL

This document is confidential. Do not disclose or use except as authorized.

	11													
	12													
	13													
	14													

	3													
	15													
	16													
	17													
	18													
	19													
	20													
	21													
	22													
	4													

CONFIDENTIAL

This document is confidential. Do not disclose or use except as authorized.

	23																						
	24																						
	25																						
	26																						
	27																						
	28																						

CONFIDENTIAL

This document is confidential. Do not disclose or use except as authorized.

Appendix 3

DEXAMETHASONE RINSE IN MUCOLOX™ FOR THE TREATMENT OF ORAL INFLAMMATORY ULCERATIVE DISEASES

VISIT #1

Subject Name _____

[figure not shown]
[figure not shown]
Medical Record Number _____

Date of Visit _____

SUBJECTIVE DATA (Over last two weeks unless specified)

MUCOSAL PATHOLOGY

- 1. Does your mouth hurt now? Y/N
- 2. Does it hurt to swallow food or drink? Y/N
- 3. How would you rate your worst mouth sensitivity over the last week?

No sensitivity

Worst sensitivity

CONFIDENTIAL

This document is confidential. Do not disclose or use except as authorized.

[figure not shown]
[figure not shown]
4. Do you avoid any foods because they make your mouth hurt?

- 0 = Not at all
- 1 = Slightly
- 2 = Moderately
- 3 = Quite a bit
- 4 = Extremely

If “yes”, what types of foods?

- a. Spicy foods
- b. Acidic foods
- c. Salty foods
- d. Hard/crunchy/crusty foods
- e. Other:

5. Do you feel that your oral intake (what you eat) is limited by your oral condition? Y/N

Not limited at all

Severely limited

Score: _____

If “Yes”, how limited do you feel it is?

- a. Partial limitation
- b. Severe limitation

6. Have you been bothered by ulcers in the mouth?

- 0 = Not at all
- 1 = Slightly
- 2 = Moderately
- 3 = Quite a bit
- 4 = Extremely

CONFIDENTIAL

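### The missed-rinse rule in both arms sets a target of four rinses a day, but the trial regimen is three

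*Combined protocol and SAP*

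**What the plan says.** The Administration paragraphs in Section 8.3.1 (Mucolox, Arm A) and Section 8.4 (commercial solution, Arm B) use the same two sentences. The first sets the schedule: "The rinses will be completed three times per day, equally spaced during awake hours". The second covers a missed rinse; the subject is asked "to attempt to make up for the missed rinse later the same day, to maintain four rinses per day". An example follows, which in Section 8.4 reads "two consecutive 5 minute rinses can be completed at night before bed".

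Elsewhere the regimen is three a day:

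- Synopsis, test product: "compounded oral solution swish and spit TID for 4 weeks". The control product has the same frequency.
- Section 2.1.1, dose calculation: "0.5 mg/rinse, 3 times/day = 1.5 mg", leading to "the maximum dose would be 10.5 mg/week".
- Section 9.2.4, text and regimen table, both arms: three a day.
- Section 9.3: "three times a day for 5 minutes at a time".
- Appendix 1, patient instructions: "You will be rinsing with your solution 3 times per day".

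The only other mention of four or more rinses is in the background on chronic graft-versus-host disease (Section 1). It reports guideline care of 4-6 times a day and is not this trial's regimen.

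**The concern.** Two adjacent sentences give different daily totals, and the second is an instruction that staff are meant to pass on to subjects. Four cannot be read as a legitimate catch-up total, because making up one missed rinse brings the day back to three. The idea of maintaining four also presupposes a four-a-day schedule that this trial does not have.

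Three things are at stake, all modest:

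- A subject who follows the rule literally takes more than the scheduled dose on that day. The exposure statement in Section 2.1.1 assumes three rinses, yet the make-up rule is followed by an assurance that it carries no known safety risk.
- Extra rinses draw on the part of the bottle meant for error and spillage.
- Section 12 (Protocol Violations) counts departure from the drug regimen as a violation. A four-rinse day after a missed rinse would meet the target in Sections 8.3.1 and 8.4 but depart from Sections 9.2.4 and 9.3, leaving staff and monitor with two standards.

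**Working it through.** **Inputs.** Dose per rinse: 5 mL x 0.1 mg/mL = 0.5 mg (Sections 2.1.1 and 9.2.4). Rinses per day: 3 (regimen) or 4 (make-up rule). Treatment: 28 days. Bottle: 480 mL, described as a four-week supply with some extra (Sections 8.3.1 and 8.4). The bottle strength printed in Appendix 1 differs from 0.5 mg/5 mL; that is a separate matter and is not used here.

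**1. Reproduce the stated maximum.** 3 x 0.5 mg = 1.5 mg a day; 1.5 x 7 = 10.5 mg a week. This matches Section 2.1.1. At four a day it would be 4 x 0.5 x 7 = 14.0 mg, so the stated figure rests on three.

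**2. Check against the supply.** Three a day needs 3 x 5 x 28 = 420 mL, which leaves 480 - 420 = 60 mL spare and fits the description of a four-week supply with extra. Four every day would need 4 x 5 x 28 = 560 mL, 80 mL more than is dispensed, and the bottle would last 480 / 20 = 24 days. The supply was therefore also planned for three.

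**3. Check the rule's own example.** A subject who takes the first rinse, misses the second, and does two at bedtime has taken 1 + 2 = 3. Reaching four would need a further rinse that nothing schedules.

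**4. Size of the literal reading.** The rule applies only on days with a missed rinse, so the relevant unit is one such day.

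- Day: 4 x 0.5 = 2.0 mg against 1.5 mg.
- Week with one such day: 6 x 1.5 + 2.0 = 11.0 mg; 11.0 / 10.5 = 1.048, or +4.8%. Each further such day adds 0.5 mg.
- Supply: 480 / 5 = 96 rinses; the schedule uses 3 x 28 = 84; 12 are spare. Each four-rinse day uses one of the 12. At 12 such days the bottle is just enough (84 + 12 = 96); at 13 it is one short (97), assuming no spillage.

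The protocol gives no rate of missed rinses, so the number of such days cannot be estimated.

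**5. Effect on the analysis.** Section 12 makes a subject unevaluable for using the treatment fewer than 2 times a day for more than 2 weeks. The choice between three and four does not touch that cut-off. The sample size in Section 13.2 does not use rinse frequency.

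**The case against.** The strongest reply is that this is a drafting slip that the document largely corrects itself. Three is stated many times, including in the sentence just before. The active instruction is to make up the missed rinse, which gives three, and the example agrees. The patient sheet has no make-up rule and no mention of four, so a subject could receive the wrong number only from staff working from Sections 8.3.1 and 8.4. The 10.5 mg figure is a worst case for a rinse that is spat out, computed from the regimen and not set as a safety limit. An extra 0.5 mg in a week has no consequence that the protocol identifies, and a shortage of supply would take 13 or more four-rinse days in 28.

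All of that stands as to size, and it is why the point is minor. It does not remove the error. The wrong number appears in the dosing section of each arm, no other text gives a make-up rule that would override it, and Section 9.3 has the investigators instruct subjects on use. A reader has to disregard the text in order to dose correctly.

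It can also be said that adding a cap of three goes beyond replacing one word. The cap only restates the three-a-day regimen. If the sponsor prefers the bare replacement, that also corrects the error.

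**Conclusion.** The concern holds. Four is a wrong number in an operative dosing rule, repeated in both arms; the intended regimen is three a day. Read literally, each affected day is 0.5 mg above schedule, and a week with one such day is 4.8% above the stated maximum. This rests on 0.5 mg per rinse and on the clause applying only after a missed rinse. How often that would happen is unknown.

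Severity is minor. The wording is identical in the two arms, so it does not by itself bias the comparison of A with B, and the endpoint, sample size and evaluability rule are unaffected.

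**What to change.** In the Administration paragraphs of Sections 8.3.1 and 8.4, replace the four-a-day target with three, for example: a missed rinse may be made up later the same day so that the day's total is three rinses, and no more than three.

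The cost is one phrase in two sections. The dose statement, supply, patient sheet, analysis and sample size need no change for this correction. The column headings of the Appendix 2 diary cannot be read in the text reviewed, so whoever makes the edit should confirm that it provides for three rinses a day.

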8.5 Study Drug Accountability

An accurate and current accounting of the dispensing and return of study drug for each subject will be maintained on an ongoing basis by a member of the study site staff. The number of study drug dispensed and returned by the subject will be recorded on the Investigational Drug Accountability Record. The study monitor will verify these documents throughout the course of the study.

8.6 Measures of Treatment Compliance

Subjects will be asked to keep a patient diary (Appendix 2) noting the day and date they take their study drug and any adverse events. They will be asked to bring their patient diary to each study visit along with all used and unused study drug containers.

9 STUDY PROCEDURES AND GUIDELINES

Prior to conducting any study-related activities, written informed consent and the Health Insurance Portability and Accountability Act (HIPAA) authorization must be signed and dated by the subject or subject's legal representative. If appropriate, assent must also be obtained prior to conducting any study-related activities.

9.1 Clinical Assessments

9.1.1 Concomitant Medications

All concomitant medication and concurrent therapies will be documented at Baseline/Screening and at Study Visits 1, and at early termination when applicable. Dose, route, unit frequency of administration, and indication for administration and dates of medication will be captured.

9.1.2 Demographics

Demographic information (date of birth, gender, race) will be recorded at Screening.

9.1.3 Medical History

Relevant medical history, including history of current disease, other pertinent respiratory history, and information regarding underlying diseases will be recorded at Screening.

9.2 Study procedures

Potentially eligible subjects will be screened by one of the investigators by asking patients to rate their worst oral pain or pain score (0-10) over the previous week on a VAS. Those answering with at least a score of “7” (1/10) and that meet all other eligibility requirements (see Section 6) will be eligible for enrollment. All patients will sign informed consent for study participation. Each study visit is anticipated to take approximately 45 minutes. A urine pregnancy test will be performed for women of child bearing potential.

There is no financial compensation for participating in this study. Treatment will be administered on an outpatient basis. Study medication will be prescribed by authorized study staff physicians and filled by the Investigational Pharmacy at no expense for the patient. No investigational or commercial agents or therapies other than those described below may be administered with the intent to treat the participant’s Oral Inflammatory Ulcerative Diseases.

Subjects will be evaluated clinically at baseline before starting treatment and at the end of the four-week period, for a total of two visits. Comprehensive subjective and objective data will be collected (Appendix 3 & 4) and intraoral photographs will be obtained. Oral mucosal disease will be evaluated using both patient reported (questions/visual analog scales) and clinician assessed measures.

Subjects will be prescribed compounded dexamethasone 0.5mg/5ml solution in Mucolox™ (ARM A) or commercial dexamethasone 0.5mg/5ml solution only (ARM B). All subjects will also receive a prescription for fluconazole 200 mg tablets once-a-week as prophylactic antifungal therapy. Any subjects that are already taking an antifungal oral medication at the time of the study enrollment will continue their prescribed medication and will not need to take the additional weekly fluconazole dose. Subjects will return for evaluation after four weeks at which time the study endpoints will be assessed.

If there is worsening of Oral Inflammatory Ulcerative Diseases that requires initiation of new immunomodulatory medications (systemic or topical), patients will remain on treatment, but will be regarded as unevaluable for the primary endpoint.

	Day 1 (baseline)	Day 28 ± 5 days (end of study)
Clinical examination	x	x
OHIP-14	x	x
Patient Reported Outcomes	x	x

9.2.1 Clinician Reported Outcomes

Mucosal disease will be measured using the REU scoring system for monitoring Oral Inflammatory Ulcerative Diseases³⁴. Assessment requires only a light source and a dental mirror. This is a validated semiquantitative instrument for monitoring reticular/hyperkeratotic, erosive/erythematous, and ulcerative OLP lesions. The oral cavity is divided into ten sites: right buccal mucosa, left buccal mucosa, tongue dorsum, tongue ventrum, maxillary gingiva, mandibular gingiva, floor of mouth, hard palatal mucosa, soft palate and tonsil, and labial mucosa (upper and lower together). The severity of each type of lesion is scored according to the presence or absence of reticulations/hyperkeratosis (0 = absent; 1 = present), and the size of the erosions/erythema or ulcers (in cm²) (0 = no involvement; 1-3 in increasing area of involvement). Because each type of lesion causes different degrees of discomfort and pain, each type of lesion is weighted accordingly: reticular lesions are weighted 1 because this presentation tends to be asymptomatic; erosive/erythematous lesions are weighted 1.5 since they tend to cause some degree of discomfort; ulcerative lesions are weighted 2.0 since they tend to be the most painful. The scores for each anatomic site are then totaled.

Intraoral photographs will be obtained at each visit.

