1.1.3 Mucolox™

Mucolox™ is a mucoadhesive polymer gel that can be used in pharmaceutical compounding for the management of diseases and conditions of the oral mucosa including oral mucositis, and mouth ulcers^{29,30}. The safety and toxicological profile of Mucolox™ was evaluated in vitro and compared to Triton X- 100 (positive control) and distilled water (negative control), using a 3-

dimensional model of the human oral mucosa. Results showed that Mucolox™ can bind to tissues six times longer than Triton X-100 (before 50% cell viability) therefore offering increased retention of medication at the site of action. Additionally, at 4.5 hours, the difference in percent cell viability between Mucolox™ and distilled water was not significant, making it a safe water-soluble mucosal delivery system.

A recent study from our group showed that commercial dexamethasone 0.5mg/5mL solution compounded with Mucolox™ was found to be a safe option for the management of oral lichen planus when rinsed three times a day for 5-minute swish and expectorate³¹. Subjects receiving dexamethasone 0.5mg/5mL solution in Mucolox™ had a better clinical response compared to dexamethasone 0.5mg/5mL commercial solution alone (6-point reduction vs. 4.3; $p < 0.001$) of reticulation/keratosis, erythema, and ulceration (REU) scores. Both arms had a subjective improvement of the oral symptoms after 4 weeks of treatment.

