This document is confidential. Do not disclose or use except as authorized.

OBJECTIVE DATA (REU score)

Site	Reticular area			Erythematous area			Ulcerative area			
	0	1	2	0	1	2	0	1	2	3
Upper/lower labial mucosa	0	1	0	1	2	3	0	1	2	3
Right buccal mucosa	0	1	0	1	2	3	0	1	2	3
Left buccal mucosa	0	1	0	1	2	3	0	1	2	3
Dorsal tongue	0	1	0	1	2	3	0	1	2	3
Ventral tongue	0	1	0	1	2	3	0	1	2	3
Floor of mouth	0	1	0	1	2	3	0	1	2	3
Hard palate mucosa	0	1	0	1	2	3	0	1	2	3
Soft palate/tonsillar pillars	0	1	0	1	2	3	0	1	2	3
Maxillary gingiva	0	1	0	1	2	3	0	1	2	3
Mandibular gingiva	0	1	0	1	2	3	0	1	2	3
Total										

(R: 0 = not present, 1 = present; E & U: 0 = not present, 1 = <1cm², 2 = 1 - 3cm², 3 = >3cm²)

Total Score:

Total Weighted Score:

PHOTOGRAPHS TAKEN (circle): YES NO

CONFIDENTIAL

This document is confidential. Do not disclose or use except as authorized.

Appendix 4

DEXAMETHASONE RINSE AND MUCOLOX™ FOR THE TREATMENT OF ORAL INFLAMMATORY ULCERATIVE DISEASES

VISIT #2

Subject Name _____

Medical Record Number _____

[figure not shown]
Date of Visit _____

SUBJECTIVE DATA (Over last one week unless specified)

MUCOSAL PATHOLOGY

- 1. Does your mouth hurt now? Y/N
- 2. Does it hurt to swallow food or drink? Y/N

3. How would you rate your worst mouth sensitivity over the last week?

No sensitivity

Worst sensitivity

4. Do you avoid any foods because they make your mouth hurt?

- 0 = Not at all
- 1 = Slightly
- 2 = Moderately
- 3 = Quite a bit
- 4 = Extremely

[figure not shown]
[figure not shown]
CONFIDENTIAL

This document is confidential. Do not disclose or use except as authorized.

If “yes”, what types of foods?

- a. Spicy foods
- b. Acidic foods
- c. Salty foods
- d. Hard/crunchy/crusty foods
- e. Other:

5. Do you feel that your oral intake (what you eat) is limited by your oral condition? Y/N

Not limited at all

Severely limited

Score: _____

If “Yes”, how limited do you feel it is?

- a. Partial limitation
- b. Severe limitation

[figure not shown]
6. Have you been bothered by ulcers in the mouth?

- 0 = Not at all
- 1 = Slightly
- 2 = Moderately
- 3 = Quite a bit
- 4 = Extremely

7. Rate your level of comfort while rinsing with the topical therapy:

[figure not shown]
CONFIDENTIAL

This document is confidential. Do not disclose or use except as authorized.

[figure not shown]
Score: _____

8. Rate the taste of the topical treatment:

Score: _____

9. Rate how your mouth feels since starting topical therapy:

Score: _____

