10. Overall, since beginning topical therapy, my mouth is: (Check one)

- Very much better
- Moderately better

CONFIDENTIAL

This document is confidential. Do not disclose or use except as authorized.

- A little better
- About the same
- A little worse
- Moderately worse
- Very much worse

CONFIDENTIAL

This document is confidential. Do not disclose or use except as authorized.

OBJECTIVE DATA

Site	Reticular area			Erythematous area			Ulcerative area			
	0	1	2	0	1	2	0	1	2	3
Upper/lower labial mucosa	0	1	2	0	1	2	0	1	2	3
Right buccal mucosa	0	1	2	0	1	2	0	1	2	3
Left buccal mucosa	0	1	2	0	1	2	0	1	2	3
Dorsal tongue	0	1	2	0	1	2	0	1	2	3
Ventral tongue	0	1	2	0	1	2	0	1	2	3
Floor of mouth	0	1	2	0	1	2	0	1	2	3
Hard palate mucosa	0	1	2	0	1	2	0	1	2	3
Soft palate/tonsillar pillars	0	1	2	0	1	2	0	1	2	3
Maxillary gingiva	0	1	2	0	1	2	0	1	2	3
Mandibular gingiva	0	1	2	0	1	2	0	1	2	3
Total										

(R: 0 = not present, 1 = present; E & U: 0 = not present, 1 = <1cm², 2 = 1 - 3cm², 3 = >3cm²)

Total Score:

Total Weighted Score:

PHOTOGRAPHS TAKEN (circle): YES NO

CONFIDENTIAL

This document is confidential. Do not disclose or use except as authorized.

CONFIDENTIAL

This document is confidential. Do not disclose or use except as authorized.

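### The REU lesion score is a visual grade by a clinician who may know the arm and, on the printed Visit 2 form, has just recorded the patient's opinion of the rinse; scoring shifts of one category are about the size of the difference seen in the preliminary study

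*Combined protocol and SAP*

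**What the plan says.** Section 8.2 states: "This is an open label trial with no blinding". Section 9.2.1 describes REU as a semiquantitative score of reticular, erythematous and ulcerative lesions. On the method it says: "Assessment requires only a light source and a dental mirror". On the extent: "The oral cavity is divided into ten sites". Reticular change is scored 0 or 1. Erythema and ulceration are each scored 0 to 3 by area, with bands of under 1, 1 to 3 and over 3 cm² on the forms in Appendices 3 and 4. The lesion types carry weights of 1, 1.5 and 2.0. Sections 5.2 and 13.1 class REU as objective, and section 13.1.2 compares its change between the arms.

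Four provisions bring the arm, or the patient's opinion of the rinse, close to the scorer:

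- Section 9.3: "The Investigator or co-investigators will prescribe the study drug in the clinic and instruct the patient on study drug use".
- Section 8.6 has patients bring their diary and study bottles to each visit, and section 5.3 has the evaluating physicians review the diary at week 4.
- Section 9.2.3 has the clinician who sees the patient complete the patient-report forms.
- Appendix 4 (Visit 2 form) places four questions about the treatment ahead of the REU grid. They run from "7. Rate your level of comfort while rinsing with the topical therapy", through taste and mouth feel, to "10. Overall, since beginning topical therapy, my mouth is: (Check one".

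Section 9.2.1 also provides for intraoral photographs at each visit. No masked assessor and no masked reading of the photographs is described.

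**The concern.** The primary endpoint is a symptom score from patients who know which rinse they used. REU is the natural corroboration, because it comes from someone other than the patient. It can do that job only if the scorer's expectations are kept out of it, and nothing in the plan does so.

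Expectation is likely to favour Arm A. Section 1.1.3 reports that the group's preliminary study found a larger REU reduction with the Mucolox product than with "commercial solution alone (6-point reduction vs. 4.3", and section 2 treats that study as having shown efficacy.

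Lesion area judged by eye in three bands leaves room for judgement near each boundary. If borderline lesions are graded leniently in one arm, the between-arm comparison carries that leniency, and the planned t-test or Mann-Whitney test cannot separate it from a treatment effect. A positive REU result would then add little independent support to the open-label symptom score.

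**Working it through.** **Inputs**

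- REU reductions in the preliminary study: 6 and 4.3 points (section 1.1.3).
- Weights: reticular 1, erythema 1.5, ulcer 2.0; ten sites (section 9.2.1).
- Patients per arm: 15 (section 13.2).
- Not given in the documents: the SD and sample size of that REU result, and whether it is the weighted or unweighted total. Weighted is assumed first.

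**Benchmark difference.** 6 - 4.3 = 1.7 points. Only this subtraction can be checked; the documents contain no data from which to re-derive the two reductions.

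**Scale.** Maximum per site = 1 + 3 × 1.5 + 3 × 2.0 = 11.5. Over ten sites the weighted score runs from 0 to 115, so 1.7 points is a small distance on it.

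**One category at one site.** Share of the benchmark = weight / 1.7. Because 1.7 is a difference between arm means, the share of patients who must be shifted by one category is 1.7 / weight if only one arm is affected. It is 1.7 / (2 × weight) of each arm if the arms are shifted in opposite directions.

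| Lesion type | Points per step | Share of 1.7 | Shift needed, one arm only | Shift needed, opposite shifts in both arms |
|---|---|---|---|---|
| Ulcer | 2.0 | 118% | 85% of that arm | 42.5% of each arm |
| Erythema | 1.5 | 88% | 113% (not reachable with one step each) | 57% of each arm |
| Reticular | 1.0 | 59% | 170% (not reachable with one step each) | 85% of each arm |

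With 15 patients in Arm A, 85% is 0.85 × 15 = 12.75, that is, about 13 patients. One erythema step in every Arm A patient gives 1.5 points, 0.2 short of 1.7.

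**If 6 and 4.3 are unweighted totals**, every one-category step is 1.0 point, or 59% of the benchmark, whatever the lesion type.

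**Effect on the test (illustration).** The SD of REU change is an assumption, ranged from 1.5 to 4. With 15 per arm, no true effect and a mean scorer shift of b points between arms, the two-sided 5% t-test (28 degrees of freedom) has non-centrality b / (SD × √(2/15)). The chance of p < 0.05 is then:

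| Mean shift b | SD 1.5 | SD 2 | SD 3 | SD 4 |
|---|---|---|---|---|
| 1.0 | 42% | 26% | 14% | 10% |
| 1.5 | 75% | 51% | 26% | 17% |
| 2.0 | 94% | 75% | 42% | 26% |

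The nominal rate is 5%. The table shows what a shift of each size would do; it is no evidence that one will occur.

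**The case against.** **Open label is a declared choice.** The trial is a 30-patient phase 2 study, REU is secondary, and the sample size does not rest on it. That limits the weight of the point. It does not answer it, because an open-label treatment does not require an unmasked scorer.

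**The stronger arithmetic does not hold.** A reader might infer that one generous grade at one site could by itself produce the whole preliminary difference. Only an ulcer step exceeds 1.7 points, and it would have to be shifted in the same direction in about 85% of Arm A. Those patients would also need an ulcer near a category boundary. The background (section 1) calls the reticular form of oral lichen planus the most common and describes little ulceration in chronic graft-versus-host disease, although entry at a sensitivity score of 7 or more may select worse disease. The benchmark comes from oral lichen planus alone, whereas this trial covers four conditions.

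**The sequence is not proven.** A reader might infer that the scorer always grades the mucosa after hearing the patient's verdict. Nothing requires the form to be worked through in printed order, and the schedule in section 9.2 lists the clinical examination first. Section 8.6 does not say that the scorer sees the diary or bottles before grading. These objections stand, so the point is conditional on the printed order being followed.

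**The photographs offer a partial check.** A masked re-read could test the live scores, so it would be wrong to say that nothing could ever detect a scorer effect. No such reading is planned, however.

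**Moving REU to the very front has a cost.** An examination of ten sites before item 3 could disturb the primary endpoint, particularly when the same clinician completes that item. This stands, and the fix is arranged to avoid it.

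**Conclusion.** The point holds as a risk of bias towards Arm A in a secondary endpoint. The documents describe an unaided visual area grade, compared between arms, with no step that keeps the scorer unaware of the arm. The printed Visit 2 form also puts the patient's opinion of the rinse just before the grade.

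One-category scoring shifts are about the size of the preliminary 1.7-point difference, but they would have to recur across most of one arm, or in opposite directions in a substantial part of both. The ulcer, erythema and reticular percentages assume that the 6 and 4.3 points are weighted scores.

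The documents do not support the further inference that REU scoring will be biased, or that the preliminary result was. They say nothing about how the preliminary study was masked. The change is worth making because it costs little and gives REU more value as corroboration of the primary symptom score.

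**What to change.** Amend section 9.2.1 and the forms in Appendices 3 and 4:

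1. **Visit 2 order.** Keep items 1-6, including item 3 (the primary endpoint), before the examination. Then score and sign the REU grid. Only after that ask items 7-10 and review the diary and returned bottles.
2. **Visit 1.** Complete and sign REU before the pharmacy releases the allocation. Section 4.1 already places the baseline evaluation before treatment, but it does not time the release of the allocation.
3. **Scorer at Visit 2.** Where an existing co-investigator who neither prescribed for nor instructed the patient is available, have that person score REU without being told the arm. Record on the CRF, for every patient, whether the scorer knew the arm.

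**Cost.** Steps 1 and 2 need form changes and a sentence or two in section 9.2.1, with no additional staff, visits or patients. Step 3 needs some clinic scheduling and depends on a second investigator being free, which the documents do not establish for this single site.

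**Limits.** Steps 1 and 2 reduce what the scorer is exposed to; they do not mask a scorer who already knows the arm. Items 1-6 still tell that clinician how symptomatic the patient is.
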